**Table 3-3 Study VX15-371-101: Treatment Period**

Event/Assessment	Treatment Period a								
	Treatment Period 1 (Day 1 to Day 28)				Washout b (Day 29 to Day 56) (+ 3 days)	Treatment Period 2 (Day 57 to Day 84)			
	Day 1	Day 3 ( $\pm$ 1 day)	Day 14 ( $\pm$ 3 days)	Day 28 (- 2 days)		Day 57	Day 59 ( $\pm$ 1 day)	Day 70 ( $\pm$ 3 days)	Day 84 (- 2 days)
Clinic visit	X		X	X		X		X	X
Telephone contact c		X					X		
Inclusion/exclusion criteria review	X								
Randomization d	X								
Height and weight f	X			X		X			X
Vital signs g	X		X	X		X		X	X
Physical examination h	X			X		X			X
Standard 12-lead ECG i	X		X	X		X		X	X

a See Section 8.1.4 for guidance about discontinuation of study drug treatment.

b The Washout Period may be for acute upper or lower respiratory infection, pulmonary exacerbation, or changes in therapy (including antibiotics) upon discussion with and approval by the medical monitor (see Section 8.1.3.2).

c A telephone contact will occur on Day 3 and Day 59 of the study for safety purposes (e.g., inquiry about adverse events).

d Randomization will occur after all inclusion and exclusion criteria are met. If the screening genotype result is not received before randomization, a previous *CFTR* genotype lab report may be used to establish eligibility. *Note: Subjects who have been randomized on the basis of a historical genotype lab report and whose screening genotype does not confirm study eligibility must be discontinued from the study.*

f Height and weight will be measured with shoes off.

g All vital signs will be collected within 60 minutes before inhaled study drug dosing. Only pulse rate and blood pressure will be collected 90 ( $\pm$  30) minutes after inhaled study drug dosing. Vital signs will be assessed after the subject has been seated or supine for at least 5 minutes (Section 11.6.3).

h An abbreviated physical examination will be performed before dosing with inhaled study drug (see Section 11.6.3).

i The ECG will be performed 60 ( $\pm$  30) minutes after completion of inhaled study drug dosing and after the subject has been seated or supine for at least 5 minutes (Section 11.6.4).

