- For all safety parameters, if there are multiple measurements within a visit window, then 1) the record closest to the target day will be used; or 2) if there are multiple records with the same distance to the target day, the earliest record will be used.

**Incomplete/Missing data:** will not be imputed, unless otherwise specified.

**Outliers:** No formal statistical analyses will be performed to detect and/or remedy the presence of statistical outliers.

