#### **9.4.4 Vital Signs**

The raw values and change from period baseline values will be summarized by treatment group at each scheduled time point for the following treatment-emergent vital signs measurements: systolic and diastolic blood pressure (mm Hg), body temperature (°C), HR (beats per minute), weight, height, BMI and respiratory rate (breaths per minute). In addition, the mean value at each time point will be plotted by treatment group for systolic and diastolic blood pressure.

The number and percentage of subjects with vital signs meeting the threshold analysis criteria during the TE period will be presented. The threshold analysis criteria are provided in Section 12.5 (Table 12-10 Threshold Criteria for Vital Signs).

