**Table 12-3 Study VX15-371-101: Treatment Period**

Event/Assessment	Treatment Period a							
	Treatment Period 1 (Day 1 to Day 28)			Washout b (Day 29 to Day 56) (+ 3 days)	Treatment Period 2 (Day 57 to Day 84)			
	Day 1	Day 3 (± 1 day)	Day 14 (± 3 days)		Day 57	Day 59 (± 1 day)	Day 70 (± 3 days)	Day 84 (- 2 days)
Clinic visit	X		X	X		X	X	X
Telephone contact c		X				X		
Inclusion/exclusion criteria review	X							
Randomization d	X							
Height and weight f	X			X		X		X
Vital signs g	X		X	X		X	X	X
Physical examination h	X			X		X		X
Standard 12-lead ECG i	X		X	X		X	X	X

a See section 8.1.4 of CSP for guidance about discontinuation of study drug treatment.

b The Washout Period may be for acute upper or lower respiratory infection, pulmonary exacerbation, or changes in therapy (including antibiotics) upon discussion with and approval by the medical monitor (see section 8.1.3.2 of CSP).

c A telephone contact will occur on Day 3 and Day 59 of the study for safety purposes (e.g., inquiry about adverse events).

d Randomization will occur after all inclusion and exclusion criteria are met. If the screening genotype result is not received before randomization, a previous *CFTR* genotype lab report may be used to establish eligibility. *Note: Subjects who have been randomized on the basis of a historical genotype lab report and whose screening genotype does not confirm study eligibility must be discontinued from the study.*

f Height and weight will be measured with shoes off.

g All vital signs will be collected within 60 minutes before inhaled study drug dosing. Only pulse rate and blood pressure will be collected 90 (± 30) minutes after inhaled study drug dosing. Vital signs will be assessed after the subject has been seated or supine for at least 5 minutes ( see section 11.6.3 of CSP).

h An abbreviated physical examination will be performed before dosing with inhaled study drug (see section 11.6.3 of CSP).

i The ECG will be performed 60 (± 30) minutes after completion of inhaled study drug dosing and after the subject has been seated or supine for at least 5 minutes ( see section 11.6.4 of CSP).

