**Table 12-6 Visit Window Mapping Rules for Safety Assessments**

Assessments	Analysis Period	Analysis Visit	Target Study Day	Visit Window (in study days)

 
• Serum and plasma chemistry
 
• Urine tests(sodium and potassium)§
 
	1	Baseline	1	[screening visit, pre-dose Day 1]
	1	Day 14	14	(1*, 21]
	1	Day 28	28	[22, 35]
	2	Baseline	1	[end of TE period for first period +1 , pre-dose Day 1]
	2	Day 14	14	(1*, 21]
	2	Day 28	28	[22, 35]
		Safety Follow-up Visit	NA	Use the nominal visit if study day greater than 35

 
• Vital signs (respiratory rate and temperature)
 
	1	Baseline	1	[screening visit, pre-dose Day 1]
	1	Day 14	14	[2, 21]
	1	Day 28	28	[22, 35]
	2	Baseline	1	[end of TE period for first period +1 , pre-dose Day 1]
	2	Day 14	14	[2, 21]
	2	Day 28	28	[22, 35]
		Safety Follow-up Visit	NA	Use the nominal visit if study day greater than 35

 
ECG
 
	1	Baseline	1	[screening visit, pre-dose Day 1]
	1	Day 1	1	1†
	1	Day 14	14	(1*, 21]
	1	Day 28	28	[22, 35]
	2	Day 1	1	1†
	2	Day 14	14	(1*, 21]
	2	Day 28	28	[22, 35]
		Safety Follow-up Visit	NA	Use the nominal visit if study day greater than 35

 
• Hematology
 
• Coagulation
 
	1	Baseline	1	[screening visit, pre-dose Day 1]
	1	Day 28	28	(1*, 35]
	2	Baseline	1	[end of TE period for first period +1 , pre-dose Day 1]
	2	Day 28	28	(1*, 35]
		Safety Follow-up Visit	NA	Use the nominal visit if study day greater than 35

Assessments	Analysis Period	Analysis Visit	Target Study Day	Visit Window (in study days)
• Weight	1	Baseline	1	[screening visit, Day 1]
	1	Day 28	28	[2, 35]
	2	Baseline	1	[end of TE period for first period +1, Day 1]
	2	Day 28	28	[2, 35]
		Safety Follow-up Visit	NA	Use the nominal visit if study day greater than 35
• Spirometry • Vital Sign (HR, SBP, and DBP)	1	Baseline	1	[screening visit, pre-dose Day 1]
	1	Day 1	1	1†
	1	Day 14	14	(1*, 21]
	1	Day 28	28	[22, 35]
	2	Baseline	1	[end of TE period for Period 1+1, pre-dose Day 1]
	2	Day 1	1	1†
	2	Day 14	14	(1*, 21]
	2	Day 28	28	[22, 35]
		Safety Follow-up Visit	NA	Use the nominal visit if study day greater than 35

\* Day 1 post-dose measurement (unscheduled) in each period

† Day 1 post-dose measurement (scheduled) in each period

§ Urine samples will also be collected post-dose on Day 14 and Day 28 in each period

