**Note:**

1. All assessments including early termination visits, safety follow-up and unscheduled visits will follow the individual visit window to be mapped to individual visits.
2. Spirometry and vital sign assessments (heart rate, systolic blood pressure and diastolic blood pressure) taken at unscheduled visits or early termination visit or safety-follow-up visits will be considered as predose measurements and follow the visit window mapping rules to derive analysis visit.

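### Applied as written, the SAP's safety record-selection rule takes postdose blood pressure and pulse at Day 1 but predose values at Days 14 and 28, so the by-visit summaries mix the two

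*SAP*

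**What the plan says.** **Collection.** Footnote g of the treatment-period schedule (Protocol Table 3-3, repeated in SAP Table 12-3) sets the predose reading: "All vital signs will be collected within 60 minutes before inhaled study drug dosing". It then adds a postdose reading for two of the signs: "Only pulse rate and blood pressure will be collected 90" (± 30) minutes after dosing. Vital signs are scheduled on Days 1, 14, 28, 57, 70 and 84.

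**Selection.** SAP 9.1 states: "For all safety parameters, if there are multiple measurements within a visit window, then 1) the record closest to the target day will be used". The tie-break is "if there are multiple records with the same distance to the target day, the earliest record will be used". Neither step mentions whether a record is predose or postdose.

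**Windows.** SAP Table 12-6 puts spirometry and "Vital Sign (HR, SBP, and DBP") in one row. In each period, baseline ends at predose Day 1. The Day 1 visit carries a dagger, explained as "Day 1 post-dose measurement (scheduled) in each period". Day 14 is (1*, 21] and Day 28 is [22, 35], both defined by study day alone.

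**Reporting.** SAP 9.4.4 says of vital signs: "The raw values and change from period baseline values will be summarized by treatment group at each scheduled time point". It also plots mean systolic and diastolic pressure. It does not mention predose or postdose.

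**The concern.** The rule pools two kinds of reading in one window and keeps one of them. At Day 1 the table forces the postdose value, while at Days 14 and 28 the tie-break returns the predose value. A reader of the blood pressure table or plot would be comparing readings taken at different times relative to dosing, with nothing to say so. A blood pressure change present after each dose but gone before the next would show at Day 1 and appear to have resolved by Day 14.

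Vital signs belong to the safety and tolerability primary endpoint (SAP 6.1), and the safety analysis is descriptive only (SAP 9.4). These tables and plots are therefore the planned by-visit analysis of blood pressure, with no model behind them that would use the remaining readings.

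**Working it through.** The plan gives no figure to reproduce. The check applies the written rule to the scheduled records.

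**Inputs**
- Visit days: Day 14 ± 3 gives 11 to 17 (7 days). Day 28 with a 2-day early allowance gives 26 to 28 (3 days). Source: Protocol Table 3-3. Period 2 is the same on its own day count, since 70 − 56 = 14 and 84 − 56 = 28.
- Reading times: predose from −60 to −10 minutes in 10-minute steps (6 values). Postdose at 90 ± 30, so 60 to 120 minutes in 10-minute steps (7 values). Source: footnote g.
- Windows: SAP Table 12-6. Selection rule: SAP 9.1.

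**Step 1: distance to target.** Distance is |study day − target day|. Both readings of a visit have the same study day, so their distances are equal whatever day the visit falls on.

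**Step 2: tie-break.** The earlier record is kept. Predose always precedes postdose, so predose is kept.

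**Step 3: all allowed combinations.** 7 × 3 × 6 × 7 = 882 schedules. Predose was selected at Day 14 in 882 of 882 and at Day 28 in 882 of 882. At Day 1 the table itself fixes postdose, again 882 of 882.

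**Step 4: what each reading of the rule keeps, per period**

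| Analysis visit | Scheduled pulse/BP records | Rule on the pooled window | Rule within predose and postdose separately |
|---|---|---|---|
| Baseline / Day 1 | predose, postdose | predose as baseline, postdose as Day 1 | both |
| Day 14 | predose, postdose | predose only | both |
| Day 28 | predose, postdose | predose only | both |
| Total kept | 6 | 4 | 6 |

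On the pooled reading, 1 of 3 postdose readings per period is used and 2 of 3 are not. Over both periods that is 4 of 6 not used (Days 14, 28, 70 and 84).

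**Step 5: the same rule on spirometry.** SAP 9.4.7.1 requires postdose ppFEV1 on Days 1, 14 and 28, and the change from predose to postdose on the same day. SAP 9.4.7.2 requires predose declines at each post-baseline visit. One record per window cannot supply both, so the rule and 9.4.7 conflict for this row.

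**The case against.** The best counter-argument is that the SAP already treats predose and postdose as separate series. Note 2 to Table 12-6 says that spirometry, heart rate and blood pressure readings from unscheduled, early-termination or follow-up visits "will be considered as predose measurements and follow the visit window mapping rules to derive analysis visit". That label has little purpose unless the two kinds of record are kept apart. Section 9.4.7.1 cannot be produced any other way, and it uses the same row. The separate Day 1 entry has an innocent explanation too: predose Day 1 is already the baseline visit. SAP 9.4.4 also asks for each scheduled time point, which could be read to include the postdose one.

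This stands as evidence of intent, but it does not supply the instruction. Note 2 covers unscheduled, early-termination and follow-up readings, and gives the scheduled postdose readings at Days 14 and 28 no analysis visit. Section 9.4.7.1 covers spirometry only; 9.4.4 has no matching sentence. The time-point phrase is also used for laboratory tests and ECG, so it does not override 9.1. Elsewhere the SAP states such distinctions outright: Table 12-5 restricts efficacy spirometry to predose, and a Table 12-6 footnote flags postdose urine samples at Days 14 and 28.

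A reader might also infer that a persistent postdose heart-rate effect would be hidden. The documents do not support that. Treatment-period ECGs are taken 60 (± 30) minutes after dosing at all six dosing visits, and SAP 9.4.3 tabulates ECG heart rate by time point and plots its mean. Section 9.4.4 plots only systolic and diastolic pressure, so there is no vital-sign pulse plot to distort.

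**Conclusion.** The point holds as a specification gap with a definite result if followed literally. The by-visit blood pressure and vital-sign pulse summaries, and the blood pressure plots, would combine postdose Day 1 with predose Days 14 and 28, and would leave out 2 of 3 scheduled postdose readings per period. For spirometry the finding is a contradiction with 9.4.7.1.

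It would go too far to conclude that these readings will certainly be missing from the report, or that data are lost. A programmer who selects within predose and postdose separately loses none. All safety data are listed (SAP 9.4), and the threshold counts over the treatment-emergent period are not stated to be limited to the selected record. Temperature and respiratory rate are taken only before dosing and are unaffected. The practical consequence is mainly for blood pressure by visit.

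The 2-of-3 figure assumes that both readings were taken on the same study day at each visit. If a predose reading is missing, the rule would take the postdose one, which would mix the two kinds within a single visit as well.

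**What to change.** 1. In SAP 9.1, state that the closest-then-earliest rule is applied separately within predose records and within postdose records, where both are scheduled.
2. In Table 12-6, add postdose Day 14 and postdose Day 28 analysis time points in each period for heart rate, systolic and diastolic pressure and safety spirometry, and label the existing Day 14 and Day 28 entries as predose.
3. In SAP 9.4.4, summarise predose and postdose pulse and blood pressure as separate series, and plot the two blood pressure series separately.

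A same-visit postdose-minus-predose change for vital signs would be a useful addition but is optional, since the protocol does not ask for it.

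The cost is a few lines of SAP text, some extra table rows and additional plots. No new data are needed, and the change can be made before database lock.

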## 9.2 Background Characteristics

Subject disposition, demographic and baseline characteristics, prior and concomitant medications, study drug exposure and compliance, and other background characteristics will be summarized using descriptive statistics for continuous variables and counts and percentages for categorical variables. Additionally, all subject data will be presented in subject data listings. All summaries will be based on the FAS unless otherwise specified. No statistical hypothesis testing will be performed on background characteristics.

### 9.2.1 Subject Disposition

The number of subjects in the run-in period who were not randomized or dosed with the inhaled study drug screen failures during the Run-in Period, number of subjects randomized or dosed with inhaled study drug, and the total number of subjects will be tabulated for the following groups and overall based on their Orkambi and HS status at Screening:

- Orkambi+/HS-
- Orkambi-/HS-
- Orkambi+/HS+
- Orkambi-/HS+

The number of subjects in the following categories will be summarized by treatment group:

- All Subjects Set (Randomized or dosed with Inhaled Study Drug)
- Randomized
- Randomized but never dosed
- Full Analysis Set (FAS)
- Safety Set

The number of subjects in the following categories will be presented by treatment group for each period (Period 1 and Period 2):

- FAS
- Safety Set

The number and percentage (based on Safety Set) of subjects in each of the following disposition categories will be presented by treatment group for each period (Period 1 and Period 2):

- Completed treatment regimen
- Prematurely discontinued the treatment regimen and the reasons for discontinuations
- Prematurely discontinued inhaled study drug and the reasons for discontinuations

- Prematurely discontinued orkambi and the reasons for discontinuations
- Prematurely discontinued the study and the reasons for discontinuations

The number and percentage (based on the overall Safety Set) of subjects in each of the following disposition categories will be presented by treatment group:

- Completed treatment regimen in both periods
- Completed study

A listing will be provided for subjects who discontinued treatment or who discontinued study, along with reasons for discontinuations.

The number and percentage of randomized subjects will be summarized by stratification factor (ppFEV1 at screening), by country and by site, using the number of subjects being randomized in each treatment sequence as the denominator. A randomization listing ordered by randomization date also will be provided.

### **9.2.2 Demographics and Baseline Characteristics**

Demographic and study baseline characteristics data will be summarized by treatment group and overall based on the FAS for each period (Period 1 and Period 2).

Demographic data will include the following:

- Age (years) at screening
- Age group at screening (12 to <18 years vs  $\geq 18$  years)
- Sex (Male and Female)
  - Female only: Child bearing potential
- Race (White, Black or African American, Asian, American Indian or Alaska Native, Native Hawaiian or Other Pacific Islander, not collected per local regulations, and Other)
- Ethnicity (Hispanic or Latino, not Hispanic or Latino, and not collected per local regulations)
- Region (Europe or North America)

Study baseline characteristics will include the following:

- Weight (kg)
- Weight-for-age z-score (subjects < 20 years at screening)
- Height (cm)
- Height-for-age z-score (subjects < 20 years at screening)
- BMI (kg/m^2)
- BMI-for-age z-score (subjects < 20 years at screening)
- ppFEV1 at Screening (<70,  $\geq 70$ )

- ppFEV1 at study baseline (<40,  $\geq$ 40 to <70,  $\geq$ 70 to  $\leq$ 90 and  $>$ 90)
- ppFEV1 at study baseline
- FEV1 (L)
- FVC (L)
- ppFVC (%)
- FEF25-75% (L/sec)
- ppFEF25-75% (%)
- FEV1/FVC
- [REDACTED]
- Orkambi and HS Use at Screening (Orkambi+/HS-, Orkambi+/HS+, Orkambi-/HS-, Orkambi-/HS+)
- Use of Dornase Alfa
- Use of inhaled antibiotic
- Use of bronchodilator
- Use of inhaled bronchodilator (short-acting only, [short-acting and long-acting] or long-acting only)
- Use of inhaled corticosteroids

### 9.2.3 Medical History

Medical history will be coded using the Medical Dictionary for Regulatory Activities (MedDRA). For the FAS, medical history will be summarized descriptively by treatment group, system organ class (SOC) and preferred term (PT) for each period (Period 1 and Period 2). The corresponding data listing also will be provided.

Ophthalmology history will be presented in individual subject data listings only.

### 9.2.4 Prior and Concomitant Medications

Medications used in this study will be coded by using the World Health Organization Drug Dictionary - Enhanced and categorized as follows:

- **Prior medication:** any medication that started before the first dose of inhaled study drug in the study, regardless of when it ended.
- **Concomitant medication:** medication continued or newly received during the TE period for Treatment Period 1 or Treatment Period 2.
- **Post-treatment medication:** medication continued or newly received after the TE period for Treatment Period 2, or between the TE periods for Treatment Period 1 and Treatment

Period 2, or after the TE period for Treatment Period 1 for subjects who do not have Treatment Period 2.

A given medication can be classified as a prior medication, a concomitant medication, a post-treatment medication, or both prior and concomitant, both concomitant and post-treatment, or prior, concomitant, and post-treatment. If a medication has a missing or partial missing start/end date or time and it cannot be determined whether the medication was taken before initial dosing, concomitantly, or post-treatment, it will be considered as prior, concomitant, and post-treatment. Details for imputing missing or partial start and/or stop dates of medication are described in Section 12.3.

For the FAS, prior medications and concomitant medications will be summarized descriptively by: 1) treatment group, preferred name (PN); and 2) treatment group, anatomic class (ATC) level 1, ATC level 2, and PN. Prior medication summaries will be by period (Period 1 and Period 2). The summary tables by treatment group and PN will be repeated to include prior and concomitant medications with a frequency of  $\geq 5\%$  at the PN level. Post-treatment medications will be listed for each subject.

### **9.2.5 Study Drug Exposure**

Exposure to inhaled study drug (i.e., duration of treatment in days) will be summarized by treatment group based on the FAS.

Duration of inhaled study drug exposure is defined as follows: last dose date of inhaled study drug – first dose date of inhaled study drug + 1 day within the treatment period, regardless of any interruption in dosing between the first and the last dose.

If the last dose date of inhaled study drug in the treatment period is missing, the subject's last available inhaled study drug administration date in that treatment period will be used for analysis purposes.

Duration of inhaled study drug exposure will be summarized by treatment using descriptive summary statistics. Duration of inhaled study drug will also be summarized by time interval ( $>0$  to  $\leq 14$  days,  $>14$  to  $\leq 28$  days, and  $>28$  days) using counts and percentages.

Study drug administration information on Orkambi will be listed.

### **9.2.6 Study Drug Compliance**

Inhaled study drug compliance within each treatment period will be calculated as follows:

$$100 \times [1 - (\text{Total number of days inhaled study drug interrupted in a treatment period}) / (\text{Duration of inhaled study drug exposure in that treatment period})]$$

The total number of days of inhaled study drug interrupted in a treatment period is defined as:

sum of (number of days of inhaled study drug interrupted in each interruption interval in that treatment period)

where number of days of inhaled study drug interrupted in each interval is defined as the interruption end date – the corresponding interruption start date + 1.

Note: A subject may have treatment interruption first, followed by decision of permanent treatment discontinuation. In such cases, last dose date is collected as the date before that treatment interruption and drug interruption would appear to be after the last dose date. For calculating compliance, the interruption end date will be restricted to the last dose date.

Inhaled study drug compliance will be summarized by treatment group using descriptive summary statistics, and will also be summarized by category ( $<80\%$ ,  $\geq 80\%$ ) using counts and percentages. A list of subjects with  $<80\%$  compliance rate will be provided.

Compliance on Orkambi will be defined as follows:

$$100 \times [(\text{Total number of days on Orkambi during the inhaled study drug exposure in a treatment period after excluding the number of days Orkambi was interrupted}) / (\text{Duration of inhaled study drug exposure in that treatment period})]$$

Note that the compliance for Orkambi will not consider the run-in period as well as the washout period. Compliance on Orkambi will be summarized using an approach similar to the inhaled study drug compliance.

Inhaled Study drug compliance and compliance on Orkambi will be summarized based on the FAS.

